8. TREATMENT PLANS

- **8.1.** Six-Months Neoadjuvant apalutamide (24 weeks)
 - 8.1.1. Subjects will be instructed to take 240 mg per day orally of apalutamide, 4 tablets (60 mg each). Apalutamide may be taken with or without food and close to the same time each day as possible.
 - 8.1.2. Study Drug Procedures
 - 8.1.2.1. Apalutamide has the chemical name (4-[7-(6-Cyano-5-trifluoromethylpyridin-3-yl)-8-oxo-6-thioxo-5,7-diazaspiro[3.4]oct-5-yl]-2-fluoro-N-methylbenzamide)
 - 8.1.2.2. Apalutamide will be provided packaged in individual bottles for patient assignment at corresponding study visits. Information on labels will comply with applicable local regulations. Site pharmacist or medically qualified staff will dispense the study treatment to each patient in accordance with the protocol.
 - 8.1.2.3. The study treatment must be stored in a secure area and administered only to patients entered into the clinical study in accordance with the conditions specified in this protocol. Bottles of study treatment should be stored at 20°C to 25°C (68°F to 77°F); excursions are permitted to 15°C to 30°C (59°F to 86°F) in the original container/closure with the cap on tightly; it should never be refrigerated. Additional information is provided in the apalutamide Investigator's Brochure.
 - 8.1.2.4. Current ICH GCP Guidelines require the investigator to ensure that study drug deliveries are received by a responsible person (e.g. pharmacist), and
 - · that such deliveries are recorded
 - that study drug is handled and stored safely and properly, and should explain the correct use/handling of the investigational product to each subject.
 - that study drug is only dispensed to study subjects in accordance with the protocol that any unused study drug is returned or standard procedures for the alternative disposition of unused study drug are followed.

Drug inventory and accountability records for the study drugs will be kept by the investigator/ pharmacist. Study drug accountability throughout the study must be documented. The following guidelines are therefore pertinent:

- The investigator agrees not to supply study drugs to any persons except the subjects in this study.
- The investigator/pharmacist will keep the study drugs in a pharmacy or other locked and secure storage facility under controlled storage conditions, accessible only to those authorized by the investigator to dispense these test drugs.
- A study drug inventory will be maintained by the investigator/pharmacist. The inventory will include details of material received and a clear record of when they were dispensed and to which subject.
- At the conclusion or termination of this study, the
 investigator/pharmacist agrees to conduct a final drug supply inventory
 and to record the results of this inventory on the Drug Accountability
 Record. It must be possible to reconcile delivery records with those of
 used and returned medication. Any discrepancies must be accounted
 for. Appropriate forms of deliveries and returns must be signed by the
 person responsible.
- Returned or expired study drug will be destroyed on site per MDACC Investigational Pharmacy policies.

Apalutamide will be provided by Janssen Scientific Affairs, LLC and will be stored and handled according to the manufacturer specifications and the pharmacy standards of operation.

8.1.3. Study Drug Dose Reductions or Discontinuation of Study Drug
In subjects who experience toxicity who cannot be ameliorated by the use of
adequate medical intervention, dose reductions can be performed. Patients
who experience a Grade 3 or greater toxicity considered to be related to
apalutamide that cannot be ameliorated by the use of adequate medical
intervention should have their treatment interrupted until the toxicity
improves to a Grade 1or baseline. Patients may subsequently be re-started
on study drug at a reduced dose as per the discretion of the Principal
Investigator. If study drug needs to be discontinued for more than 30 days
due to toxicities, the patient should be discontinued from the study treatment
phase, all pre-op visit procedures should be followed, and the patient
scheduled to undergo surgery as soon as recommended by medical team.

Apalutamide Dose Levels

Dose Level	Total Daily Dose	Number of 60 mg Tablets (QD)
0	240 mg	4
-1	180 mg	3
-2	120 mg	2

- 8.1.4. Medications—Drugs and Therapies
 - 8.1.4.1. Medication taken within four weeks prior to treatment initiation must be captured in the medical record. All concomitant medications will be documented at each visit while patient is taking apalutamide, and at the time of early study treatment discontinuation. Only adjuvant/salvage therapies will be documented during the follow-up phase of the study. Standard concomitant medications associated with surgery and post-op care will not need to be captured for the purpose of this study unless it is given to treat a reportable AE.
 - 8.1.4.2. No other new systemic therapy or new radiotherapy for treatment of prostate cancer is permitted while subject is on the active phase of study treatment or prior to surgery. Adjuvant/salvage therapies after surgery could be initiated if necessary at the discretion of the treating physician.
 - 8.1.4.3. As a class effect, AR antagonists have been associated with seizures due to an off-target mechanism of action (gamma amino butyric acid chloride channel [GABAA] inhibition). Drugs known to lower the seizure threshold or cause seizures are prohibited and a representative list is included below. A medication list review must be done by the clinical team if the patient is on medications from the below class list:
 - Atypical antipsychotics (e.g. clozapine, olanzapine, risperidone, ziprasidone)
 - Bupropion
 - Lithium
 - Meperedine and pethidine
 - Phenothiazine antipsychotics (eg, chlorpromazine, mesoridazine, thioridazine)
 - Tricyclic antidepressants (eg, amitriptyline, desipramine, doxepin, imipramine, maprotiline, mirtazapine.
 - 8.1.4.4. Medications/Supplements, which are NOT RECOMMENDED while on study (monitor for increased toxicity/potential drug interactions):
 - Apalutamide (and its main metabolite, ARN000308) are metabolized primarily by human CYP3A4 or CYP2C8, thus coadministration with any of the following agents has the potential to affect the PK of apalutamide and alternative therapies should be used when available:
 - Strong CYP3A4 inhibitors: itraconazole, clarithromycin, erythromycin, diltiazem, verapamil, delavirdine, atazanavir, indinavir, nefazodone, nelfinavir, ritonavir, saquinavir, telithromycin, voriconazole, grapefruit; coadministration with any of these agents may increase apalutamide plasma concentrations

- Strong CYP3A4 inducers: phenytoin, carbamazepine, rifampin, rifabutin, rifapentin, phenobarbital, efavirenz, tipranivir, St. John's wort; co-administration with any of these agents may decrease apalutamide plasma concentrations
- Strong CYP2C8 inducers: rifampin
- Apalutamide may also induce CYP3A4; therefore, caution should be taken when administered in conjunction with CYP3A4 substrates that have a narrow therapeutic index
- Apalutamide may also induce other PXR-regulated enzymes and transporters such as CYP2C8, CYP2C9, CYP2C19, UDP glucuronosyl transferase (UGT), and P-glycoprotein.
 Coadministration of apalutamide withsubstrates of CYP3A4, CYP2B6 (eg, efavirenz, bupropion), CYP2C8 (eg, repaglinide, pioglitazone), CYP2C9 (eg, warfarin, tolbutamide), CYP2C19 (eg, omeprazole, lansoprazole), UGT (eg, levothyroxine, valproic acid) and P-glycoprotein (eg, digoxin, dabigatran etexilate, colchicine) may result in decreased concentrations and loss of efficacy.
- The potential for drug-drug interaction between apalutamide and warfarin (e.g., Coumadin) is unknown at present. If a patient is taking warfarin, re-assess PT/INR as clinically indicated and adjust the dose of warfarin accordingly.
- Due to possible resistance mechanisms which may be contributed by glucocorticoid receptor signaling, concurrent use of corticosteroids during the study is not recommended; short term use (≤ 4 weeks) will be allowed if clinically indicated, however, its use must be tapered off as soon as possible.
- Avoid pomegranate

Reference for a comprehensive list of potential drug to drug interactions:

http://medicine.iupui.edu/clinpharm/ddis/main-table/

- 8.1.4.5. Treatment Compliance: Study drug accountability will be performed to document compliance with the dosing regimen. Subjects will be asked to bring back all remaining study drug at each study visit for drug accountability.
- 8.1.4.6. Emergency Procedures and Overdose: There is no specific antidote for an overdose of apalutamide. Patients who develop adverse reactions from a suspected overdose should receive appropriate symptomatic treatment.

8.2. ADVERSE EVENTS

Timely, accurate, and complete reporting and analysis of safety information from clinical studies are crucial for the protection of subjects, investigators, and the sponsor, and are mandated by regulatory agencies worldwide.

8.2.1. Adverse Event Definitions and Classifications

Adverse Event

Adverse Event (AE) – Any untoward or unfavorable medical occurrence in a human subject, including any abnormal sign (for example, abnormal physical exam or laboratory finding), symptom, or disease, temporally associated with the subject's participation in the research, whether or not considered related to the subject's participation in the research in which a subject is administered a medicinal (investigational or non-investigational) product. An adverse event does not necessarily have a causal relationship with the treatment.

This includes any occurrence that is new in onset or aggravated in severity or frequency from the baseline condition, or abnormal results of diagnostic procedures, including laboratory test abnormalities.

Expected AE - Any AE with specificity or severity that is consistent with the current Investigator Brochure (IB) or consistent with the risk information described in the Informed Consent Document (ICD) or general investigational plan.

Serious Adverse Event

Serious Adverse Event (SAE) – Any AE associated with the subject's participation in research that:

- results in death;
- is life-threatening, (places the subject at immediate risk of death from the event as it occurred). An adverse event or suspected adverse reaction is considered "life-threatening" if, in the view of Principal Investigator, its occurrence places the patient or subject at immediate risk of death. It does not include an adverse event or suspected adverse reaction that, had it occurred in a more severe form, might have caused death;
- results in inpatient hospitalization or prolongation of existing hospitalization;
- results in persistent or significant disability/incapacity;
- is a suspected transmission of any infectious agent via a medicinal product

- results in a congenital anomaly/birth defect; or
- Important medical events that may not result in death, be life-threatening, or require hospitalization may be considered a serious adverse drug experience when, based upon appropriate medical judgment, they may jeopardize the patient or subject and may require medical or surgical intervention to prevent one of the outcomes listed in this definition. Examples of such medical events include allergic bronchospasm requiring intensive treatment in an emergency room or at home, blood dyscrasias or convulsions that do not result in inpatient hospitalization, or the development of drug dependency or drug abuse (21 CFR 312.32).
- Important medical events as defined above may also be considered serious adverse events. Any important medical event can and should be reported as an SAE if deemed appropriate by the Principal Investigator or the IND Sponsor, the IND Office.

NOTE: DEATH FOR ANY REASON SHOULD BE REPORTED AS A SERIOUS ADVERSE EVENT.

Hospitalization

For reports of hospitalization, it is the sign, symptom or diagnosis which led to the hospitalization that is the serious event for which details must be provided.

Any event requiring hospitalization or prolongation of hospitalization that occurs during the study must be reported as a serious adverse event, except hospitalizations for the following:

- Hospitalizations not intended to treat an acute illness or adverse event (e.g., social reasons such as pending placement in long-term care facility)
- Surgery or procedure planned before entry into the study. [Note:
 Hospitalizations that were planned before the start of data collection and
 where the underlying condition for which the hospitalization was planned has
 not worsened will not be considered serious adverse events. Any adverse
 event that results in a prolongation of the originally planned hospitalization is
 to be reported as a new serious adverse event.]

Life-Threatening Conditions

Disease progression should not be recorded as an adverse event or serious adverse event term; instead, signs and symptoms of clinical sequelae resulting from disease progression/lack of efficacy will be reported if they fulfill the serious adverse event definition.

Unexpected (Unanticipated) AE - Any AE, with specificity or severity that is not consistent with the current IB, or the applicable product reference safety information, or not consistent with the risk information described in the informed consent document or general investigational plan.

8.2.2. Attribution Definitions

The following classification will be used to determine whether an AE is related to the study drug, CT-011:

- Definite It is clearly related
- Probable It is likely related
- Possible It may be related
- · Unlikely It is doubtfully related
- Unrelated It is clearly NOT related

Definitely related – Events directly or indirectly attributed to study drug, and/or study participation. Events occurring with sufficient frequency to suggest that they are not random. The event follows a temporal sequence from the time of drug administration and follows a known response pattern to the study drug. It occurs immediately following the study drug administration, improves on stopping the drug, or reappears on repeat exposure.

Probably related – The event follows a reasonable temporal sequence from the time of drug administration, and follows a known response pattern to the study drug and cannot be reasonably explained by other factors. There is a reasonable response to withdrawal of the drug. Rechallenge information is not available or advisable.

Possibly related – The event has a reasonable temporal relationship to the study drug administration and follows a known response pattern to the study drug. However, a potential alternate etiology may be responsible for the event. The effect of drug withdrawal is unclear. Rechallenge information is unclear or lacking.

Unlikely – The adverse event is doubtfully related to the investigational agent.

Unrelated – Events that would occur regardless of study participation, including events that are clearly random occurrences. If the frequency of the event suggests a possible connection to the study intervention, then it should be considered related. If the event is clearly related to other factors, such as a patient's clinical

state, therapeutic interventions, or concomitant medications, the event would be considered unrelated to therapy.

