6.2 Analysis Plan

All patients who receive at least 9 weeks of neoadjuvant therapy of apalutamide and undergo radical prostatectomy will be evaluable for the primary endpoint of APRF. The proportion of patients with APRF will be estimated by the number of patients with APRF divided by the total number of evaluable patients. As a primary analysis, we will estimate this proportion along with the exact 95% confidence interval. All patients who receive any dose of apalutamide will be evaluable for safety. Toxicity data will be summarized by category, grade and attribution. Frequency distributions, graphical techniques and other descriptive measures will form the basis of the analysis of safety data.

The proportion of patients having clinical complete responses and "near" complete responses will be estimated, along with the exact 95% confidence interval. The molecular features of the treated patients will be characterized using descriptive statistics and their association with the primary endpoint, APRR, or

clinical response will be assessed through logistic regression analyses. The Kaplan-Meier method will be used to assess time to biochemical recurrence and to estimate the rate of biochemical recurrence at various time points. The EPIC quality of life data will be summarized by domains and will be compared pre- and post-treatment using paired t-test or Wilcoxon signed rank test as appropriate.

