All events occurring during the conduct of a protocol and meeting the definition of a SAE must be reported to the IRB in accordance with the timeframes and procedures outlined in "The University of Texas M. D. Anderson Cancer Center Institutional Review Board Policy for Investigators on Reporting Unanticipated Adverse Events for Drugs and Devices". Unless stated otherwise in the protocol, all SAEs, expected or unexpected, must be reported to the IND Office, regardless of attribution (within 5 working days of knowledge of the event).

All life-threatening or fatal events, that are unexpected, and related to the study drug, must have a written report submitted within **24 hours** (next working day) of knowledge of the event to the Safety Project Manager in the IND Office.

Unless otherwise noted, the electronic SAE application (eSAE) will be utilized for safety reporting to the IND Office and MDACC IRB.

Serious adverse events will be captured from the time of the first protocol-specific intervention, until 30 days after the last dose of drug, unless the participant withdraws consent. Serious adverse events must be followed until clinical recovery is complete and laboratory tests have returned to baseline, progression of the event has stabilized, or there has been acceptable resolution of the event. Additionally, any serious adverse events that occur after the 30 day time period that are related to the study treatment must be reported to the IND Office. This may include the development of a secondary malignancy.

Reporting to FDA:

Serious adverse events will be forwarded to FDA by the IND Sponsor (Safety Project Manager IND Office) according to 21 CFR 312.32.

It is the responsibility of the PI and the research team to ensure serious adverse events are reported according to the Code of Federal Regulations, Good Clinical Practices, the protocol guidelines, the sponsor's guidelines, and Institutional Review Board policy.

Maintenance of Safety Information:

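### The full definitions of all three related grades for adverse events require a known response pattern, so a first case of a new type of reaction fits none of them

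*Combined protocol and SAP*

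**What the plan says.** Section 8.2.2 gives five grades, first as one-line labels and then as full definitions. The three related grades share one requirement, joined to timing by the word *and*:

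- Definite: "The event follows a temporal sequence from the time of drug administration and follows a known response pattern to the study drug".
- Probable: the event "follows a known response pattern to the study drug and cannot be reasonably explained by other factors", in addition to reasonable timing and a response to withdrawal.
- Possible: "The event has a reasonable temporal relationship to the study drug administration and follows a known response pattern to the study drug".

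The one-line label is wider: "Possible It may be related". Unlikely means that the relation is doubtful. Unrelated means that the event would have happened anyway.

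Two sentences refer to frequency. The Definite paragraph mentions events too frequent to be random. The Unrelated paragraph says that an event whose frequency points to the intervention should be treated as related.

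The definitions are meant to be used. The list of items to record in 8.2.4 requires the relationship to study drug as set out earlier in the section.

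Several rules use the grade. Section 6.2 states: "Toxicity data will be summarized by category, grade and attribution". Section 8.2.4 states: "All life-threatening or fatal events, that are unexpected, and related to the study drug, must have a written report submitted within" 24 hours, to the IND Office. The same section asks for serious events after the 30-day window to be reported to that office if they are related, and adds: "This may include the development of a secondary malignancy". Section 8.2.1 defines an unexpected event as "Any AE, with specificity or severity that is not consistent with the current IB" or with the other safety information listed there.

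**The concern.** Possible should catch uncertain cases. Because it also requires a known pattern, a reaction of a type not yet recognised for apalutamide has no related grade to go to the first time it appears. Yet 8.2.4 needs exactly that combination for its fastest IND Office report: unexpected and related. An event that is unexpected in type can hardly also follow a known pattern.

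Safety and tolerability is a secondary objective, and section 2.5 says that apalutamide is still investigational in this setting. Attribution of new kinds of event therefore matters. Two assessors could also grade the same event differently, one working from the short label and the other from the full definition.

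**Working it through.** The plan gives no figure on this point, so the check is mainly a reading of the text.

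**Step 1. Apply the scale to one hypothetical event.** Take a life-threatening event in week 6, of a type not known for the drug, with no other evident cause, that improves when the drug is stopped. It is the only such case.

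| Grade | Test | Result |
|---|---|---|
| Definite | timing and known pattern | timing met, pattern not met |
| Probable | timing, known pattern, no other explanation, response to withdrawal | all met except pattern |
| Possible | timing and known pattern | timing met, pattern not met |
| Unlikely | relation is doubtful | not met on these facts |
| Unrelated | would have occurred regardless | not met on these facts |

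No full definition fits. The scale has a gap, and the assessor must set one sentence aside to give any grade.

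**Step 2. Trace the rules that could use the grade.**

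| Rule | Depends on relatedness? | Consequence for this event |
|---|---|---|
| Recording of adverse events (8.2.4) | No | recorded |
| Toxicity summary (6.2) | Split by attribution | shown, possibly in the wrong column |
| Serious events to the IND Office, 5 working days (8.2.4) | No | reported |
| Serious events to the company, 24 hours (8.2.4) | No | reported |
| Written report to the IND Office, 24 hours (8.2.4) | Yes | can be missed |
| Serious events after day 30 to the IND Office (8.2.4) | Yes | can be missed if the event is late |
| Dose interruption wording (8.1.3, and dose modification under 8.2.4) | Yes | depends on the grade given |
| Extreme toxicity (TOX) in the stopping rule (6.3) | Only for death before surgery | an event preventing surgery counts regardless |

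**Step 3. How far do the frequency sentences help?** They need recurrence. Inputs: *n* = 45, the maximum enrolment in section 6, and a true incidence *p* of the new reaction. The plan gives no *p*, so the values below are assumptions.

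- P(at least one case) = 1 − (1 − p)^45
- P(exactly one case) = 45 p (1 − p)^44
- P(single case, given that it is seen) = the second divided by the first

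| Assumed p | P(at least one) | P(exactly one) | P(two or more) | P(single case, given seen) |
|---|---|---|---|---|
| 1% | 0.364 | 0.289 | 0.075 | 0.289 / 0.364 = 0.79 |
| 2% | 0.597 | 0.370 | 0.227 | 0.370 / 0.597 = 0.62 |
| 5% | 0.901 | 0.236 | 0.665 | 0.236 / 0.901 = 0.26 |
| 10% | 0.991 | 0.044 | 0.948 | 0.044 / 0.991 = 0.04 |

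Within this trial, the frequency sentences give little protection for a rare new reaction and good protection for a common one. Even for a common one, they cannot help when the first case is graded.

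**The case against.** The strongest reply is that no sensible investigator would apply the text so literally. Section 8.2.4 leaves attribution to the principal investigator or a physician designee. The short label for Possible is wide enough. The Definite paragraph opens with a sentence that has no pattern condition. A known pattern need not mean one listed in the Investigator's Brochure: section 8.1.4.3 itself reasons from a class effect. Frequency need not be assessed only within these 45 patients.

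Much of this stands as a limit on the point. It does not remove it. The opening sentence of Definite says only that the event is attributed to the drug, which is the question to be answered. A class effect is still a known pattern, so it does not help with a reaction that is new to the class. The wide label shows that the section disagrees with itself, and the plan should not rely on assessors choosing the right half.

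A reader might infer more than the documents support:

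- *That such events must be graded Unlikely.* That grade has its own test, and an event with convincing timing and withdrawal response does not meet it.
- *That the safety tables miss the event.* All adverse events are recorded, and 6.2 summarises every attribution.
- *That a related-toxicity rate is biased low.* The plan names no such rate as an endpoint or test; safety analysis is descriptive.
- *That a late secondary malignancy cannot be reported.* Section 8.2.4 names it as an example. The two sections conflict, and 8.2.2 does not clearly prevail.
- *That the 24-hour IND Office route is empty.* An event unexpected only in severity can still follow a known pattern.

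**Conclusion.** The point holds as an internal inconsistency in 8.2.2, and between 8.2.2 and 8.2.4. Read literally, a first or single case of a new type of reaction fits no related definition. Three consequences follow: it may appear under the wrong attribution in the 6.2 summary, it may miss the 24-hour IND Office report and arrive within 5 working days instead, and after day 30 it may not be reported to that office at all.

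The size is modest. The primary endpoint and sample size are untouched, and so are the TOX stopping boundaries. The attribution-free routes cover serious events within the collection window. The conclusion assumes that assessors follow the full definitions, as the recording list in 8.2.4 directs. The single-case probabilities also rest on the assumed incidences and on counting within this trial only.

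Section 8.2.2 also calls the study drug CT-011, not apalutamide. This suggests, without proving it, that the text was not adapted to this trial.

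**What to change.** Amend 8.2.2 as follows.

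1. In *Possibly related*, remove the known-pattern condition. Reasonable timing would be enough, with the existing allowance that another cause may be responsible.
2. In *Probably* and *Definitely related*, make a known pattern a supporting criterion and not a required one, alongside improvement on withdrawal or recurrence on re-exposure. Absence of another explanation should not be listed as an alternative to the pattern in Probable, because that grade already requires it.
3. State that an event type absent from the Investigator's Brochure can be graded related.
4. Reconcile the short labels, the full definitions and the two frequency sentences with the reporting rules in 8.2.4.

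The cost is a few sentences in an amendment and somewhat more events graded possibly related, so the attribution table will look less favourable. With daily dosing for 24 weeks, many on-treatment events could claim reasonable timing. The documents do not allow the increase to be calculated. A wider definition also reaches the dose-interruption wording in 8.1.3 and 8.2.4 and the treatment-related death component of TOX in 6.3. The sponsor should reconcile these when the definition changes.
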